## **5 STUDY EVALUATIONS AND MEASUREMENTS**

### **5.1 Screening and Monitoring Evaluations and Measurements**

#### **5.1.1 Parental Adversity (ACE)**

The 9 ACE questions query adults as to their exposure to 9 different adverse childhood experiences (economic hardship, domestic violence, parent mental health, discrimination, parent substance abuse, divorce, parent death, parent incarceration, and neighborhood violence) and are contained in the 2011-12 National Survey of Children's Health, a nationally representative telephone survey.

#### **5.1.2 Parental Health Literacy (SAHL)**

The Short Assessment of Health Literacy (SAHL) is a validated measure of health literacy for English- and Spanish-speaking populations.

#### **5.1.3 Parental Depressive Symptoms (EPDS)**

The Edinburgh Postnatal Depression Scale (EPDS) is a validated 10-item scale for postpartum depression symptoms with scores  $\geq 9$  having a sensitivity of 97% and specificity of 43% for major or minor depression.

#### **5.1.4 Reading Activity (StimQ)**

The StimQ is an office measure of cognitive stimulation at home available in Spanish and English, and the Read subscale of the StimQ contains questions on the frequency of parent-child reading activity and the number and variety of books at home. Psychometric analysis of the StimQ shows high internal consistency (Cronbach's Alpha=0.89) and test-retest reliability ( $r=0.84$ ) and moderate correlation with the Bayley Scales of Infant Development ( $r=0.52$ ,  $p<0.001$ ).

#### **5.1.5 Reading Practices (ERPQ)**

A series of questions designed by the study team to get a better understanding of the reading practices between parents and their babies.

#### **5.1.6 Language Development (BSID-III)**

The Bayley Scales of Infant Development, Third Edition (BSID-III) is a validated, examiner-administered assessment of cognitive, language, and motor development. It is designed for children 1 to 42 months of age.

#### **5.1.7 Dialogic Reading Practices (DialogPR-Infant)**

The DialogPR-I is a pilot measure, expanding upon the DialogPR, previously validated in children 3-4 years old. This series of parent self-report questions assesses parent self-reported dialogic reading practices. This Infant subscale is modified from the main, validated scale to

incorporate non-verbal parent/child dialogic reading interactions, and will be piloted with all enrolled participants, either at the second study visit, or at their video sub-study visit, whichever comes first.

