#### Study Interventions and Measures:

In this intervention, parent-infant dyads randomized to the digital arm will receive developmentally appropriate e-books. Those randomized to the standard arm will receive developmentally appropriate board books. Participants will receive either the e-book or board book for their 6, 9 and 12 month well visits. The developmentally appropriate books selected for each of the 3 well visits are as follows: [name] *Hop on Pop* for the 6 month well visit, Sandra Boynton's *Barnyard Dance* for the 9 month well visit, and Margaret Wise' *Goodnight Moon* for the 12 month well visit.

In addition to the books, parent-infant dyads in both arms will be provided information on the importance of early parent-child reading activity by pediatric clinicians using the Reach Out and Read framework.

We will collect standard measures of demographics (child age, sex, race/ethnicity, maternal age, family structure, maternal education level, and family income category), maternal adversity (9 ACE questions), maternal health literacy (SAHL), and maternal depressive symptoms (EPDS) at baseline. About 1 month after the infant has, or is age-eligible for, their 6 and 9 month well visits we will collect measures of reading activity (StimQ and ERPQ). Roughly 1 month after the infant has, or is age eligible for, their 12 month well visit, the infant will receive a developmental assessment (BSID-III), along with additional measures of reading activity (StimQ, ERPQ). They will additionally complete the paper-based DialogPR-I at this visit. A video recorded reading task will be obtained for up to 40 participants. These participants will be asked preliminary questions about their reading practices at home at the time of the video session.

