Participants in both study arms will be followed every 3 to 4 months until the infants are between the ages of 12 and 18 months, 30 days. Information on reading activities and developmental outcomes will be collected in concert with scheduled well child visits. Differences in reading activities and developmental outcomes will be assessed between groups using intention-to-treat analysis. Parents will complete measures of demographics, health literacy, and maternal depressive symptoms at baseline. Parents will also complete measures of reading activity with their infant about 1 month after the child has, or is age-eligible for, their 6, 9, and 12 month well visits. The infant will also receive a developmental assessment at the second study visit which will happen about 1 month after they have, or are age-eligible for, their 12 month well visit. At this time the infant should be between 12 and 18 months, 30 days old. Secondary data to address these study questions does not exist, which will necessitate the collection of new data as proposed here. We anticipate that this collection of rich new data will support a careful assessment of the effects of digital vs. standard literacy promotion. The HER will be reviewed for children in both arms to count the number of well child visits and examine their vaccination history.

We anticipate collecting this data in conjunction with well child visits. In our experience, low-income families can be difficult to reach for study visits, even with appropriate study incentives. By coordinating data collection with the 6, 9, and 12 month well child visits timeframes, we can increase the probability of families attending both the well visits (to receive the Reach Out and Read Program materials) and the study visits (to collect measures of reading activity and development). In a previous study of 2100 children enrolled in a study of developmental screening, we were able to achieve a >90% follow-up rate by coordinating data collection with well child visits. In addition, our research staff can check the clinic schedule to ensure families have made timely well child visit appointments and then make reminder calls to families prior to these visits to encourage parents to attend. Study visits will be held at a location that is preferred

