### **3.1.2 Video Sub-study**

Up to 40 participants will be additionally recruited to participate in an interview and video recorded reading task. Participants will be recruited both from the larger RCT as well as from external sources (see Section 8.4). Dyads enrolled in the randomized control trial who agreed to participate in the sub-study at the time of their initial consent, and who are in the control (Traditional board book) arm, will be approached by telephone call, or the method of communication that they prefer, immediately following the time that they become age-eligible for their 9-month well visit. Participants meeting eligibility criteria and recruited external to the randomized control trial will be approached for participation at clinic appointments at one of the study sites. Participants will be continuously recruited until either the enrollment goal (40 dyads) is reached or until saturation of themes is achieved for this qualitative sub-study. Sessions, lasting approximately 45 minutes, will be held at a location that is preferred and most convenient for the parent, including but not limited to: the clinic, a separate CHOP-based facility, the Temple Infant and Child Lab, or another location based on availability and parent preference. For participants recruited from the larger study, no additional demographic data will be collected, as it will be accessed from the previously reported data. Participants recruited externally for the sub-study will complete the demographic and screening questionnaires that were previously collected by the larger study participants upon enrollment. These externally recruited participants will not participate in or be consented for participation in the larger randomized control trial.

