### **3.1.3.2 Video Sub-study**

Children will be eligible to participate in this sub-study if they were born  $\geq 35$  weeks estimated gestational age, without neurodevelopmental disabilities or congenital malformations, with Medicaid insurance (proxy measure for poverty), and, for participants being recruited externally, at least 9 months and 0 days and no more than 12 months and 0 days at the time of enrollment. As in the randomized control trial, children who are born premature  $< 35$  weeks EGA, who have neurodevelopmental disabilities, or who have congenital malformations will be excluded, as they are at increased risk of language delays. In addition, we will exclude families who do not speak English for this sub-study, as resources are not available in this pilot to execute and code video data in additional languages.

Potential subjects will be identified from 1) participants in the randomized control trial that previously consented to participate in the sub-study, were randomized into the control group (traditional board book arm), and are age-eligible for their 9 month well visit, and 2) eligible patients recruited from the Cobbs Creek clinic who are 9 to 12 months old. For participants recruited external to the randomized control trial, study staff will identify eligible participants and, when on-site at the time of the appointment, approach participants in person at the clinic before or after their appointment with the clinician. At that time, a member of our study staff will explain the study procedures and consent the parent and infant for participation. The consenting process will include a discussion of study rationale, procedures, measures, benefits, risks, and alternatives to participation. Once they have consented to participate, they will complete a demographic questionnaire (Appendix 1), questionnaires about adverse childhood experiences (Appendix 2) and health literacy (Appendix 3), and the Edinburgh Postnatal Depression Scale (EPDS) (Appendix 4). They will also schedule the parent and child for a study visit at that time if the parent is able. Parents who are unable to be scheduled for participation at that time will be contacted by study staff via telephone to schedule the study visit.

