#### **6.2 Secondary Endpoints**

Secondary endpoints will be the difference in StimQ scores, and the information about reading practices and activities from the ERPO, collected approximately 1 month after the infant has, or is age-eligible for, their 6, 9, and 12 month well visits for the randomized control trial, the DialogPR-I collected between 9 and 18 months, 30 days, as well as themes derived from the transcripts of the video and audio-recordings in the Video Sub-study. The Video Sub-study is contributing to the main study's exploration of dialogic reading behaviors when comparing e-

books to standard board books, and determining the comparative effectiveness of digital literacy promotion to standard literacy promotion on parent-child language interaction and parent reading behaviors.

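### Section 5.1.7 would have some board-book families, but no digital-arm families, complete DialogPR-I at an earlier visit, and it conflicts with the schedule in the abstract and section 4.2

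*Combined protocol and SAP*

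**What the plan says.** All references are to the combined protocol and SAP.

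- **When the form is completed, section 5.1.7.** Every enrolled participant completes DialogPR-I once, "either at the second study visit, or at their video sub-study visit, whichever comes first".
- **When the form is completed, elsewhere.** The abstract (Study Interventions and Measures) describes the visit after the 12-month well visit and says: "They will additionally complete the paper-based DialogPR-I at this visit". It makes no exception for filmed families. Section 4.2 also lists DialogPR-I at the second visit without exception, and separately has sub-study families complete it at the video visit.
- **Who attends the video visit.** Section 3.1.2 limits trial families to those "who are in the control (Traditional board book) arm, will be approached by telephone call", with contact made "immediately following the time that they become age-eligible for their 9-month well visit". Section 3.1.3.2 repeats the limit: trial candidates are those who "were randomized into the control group (traditional board book arm), and are age-eligible for their 9 month well visit". Other sub-study families are recruited outside the trial.
- **When the second visit takes place.** Section 3.1.1 places the developmental assessment "at the second study visit which will happen about 1 month after they have, or are age-eligible for, their 12 month well visit".
- **Status of the measure.** Section 6.2 includes "the DialogPR-I collected between 9 and 18 months, 30 days" among the secondary endpoints. Section 5.1.7 calls it a pilot measure. Section 6.3 names no analysis for it.

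**The concern.** Under section 5.1.7, the occasion on which this endpoint is measured is fixed after randomisation and depends on arm. A filmed board-book family answers at the video visit and not again. Every digital-arm family answers at the second visit.

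The two occasions differ in child age. They also differ in type: one is a filmed reading session with three versions of a book and an interview about reading, the other a visit with a developmental assessment. The earlier occasion also tends to come before the third book, which is tied to the 12-month well visit.

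Intention-to-treat analysis does not repair this, because the imbalance lies in how the outcome is measured and not in who is analysed. Filmed controls would also have no second-visit form, and that gap cannot be filled at analysis.

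The three scheduling statements cannot all be followed. Section 5.1.7 gives a filmed control one form; section 4.2 gives two. The window in section 6.2 opens at 9 months and so admits either occasion, without saying which record is the trial endpoint.

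**Working it through.** **1. The plan's own sample size.** Section 6.3 and Figure 1 give 100 children, 50 per arm, for a 7.5-point BSID-III difference with SD 15, alpha 0.05 (taken as two-sided) and power 0.70. Standard error = 15 × √(2/50) = 3. Then 7.5/3 = 2.5, and 2.5 − 1.96 = 0.54, which gives power 0.705. The figure reproduces and is not in dispute. It supplies the 50 per arm used below.

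**2. Share measured early if section 5.1.7 is followed.** Let k be the number of filmed board-book trial families; the plan does not state k.

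- Digital arm: 0 of 50.
- Board-book arm: k of 50. The sub-study takes up to 40 dyads, so the ceiling is 40/50 = 80%. Reaching it would need no external recruits, and these count toward the same 40.

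**3. Gap between the two occasions.**

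- Filming: 9 to 12 months (abstract, Study Design; section 6.3).
- Second visit: 12 + 1 = about 13 months (section 3.1.1).
- Gap: from 13 − 12 = 1 month to 13 − 9 = 4 months. Filming at 10.5 months, an assumed midpoint, gives 2.5 months.

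**4. Difference in mean child age at DialogPR-I.** Formula: (k/50) × gap, assuming second visits fall at the same age in both arms.

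| Filmed controls k | k/50 | Gap 1 month | Gap 2.5 months | Gap 4 months |
|---|---|---|---|---|
| 10 | 0.2 | 0.2 | 0.5 | 0.8 |
| 20 | 0.4 | 0.4 | 1.0 | 1.6 |
| 40 (ceiling) | 0.8 | 0.8 | 2.0 | 3.2 |

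The second visit may take place up to 18 months, 30 days. Each month that it falls after 13 months adds k/50, that is 0.2, 0.4 or 0.8 months.

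**5. The same quantity if section 4.2 is followed and the second-visit form is analysed.** Every trial family has that form, so the video visit contributes no age difference.

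**6. Is a between-arm comparison intended?** Aim 2 (section 2.2) compares reading behaviours between e-books and board books. Section 3.1.1 says: "Differences in reading activities and developmental outcomes will be assessed between groups using intention-to-treat analysis". Section 4.2 groups DialogPR-I with StimQ and ERPQ as a reading-activity measure. Together these imply a comparison, but no passage names one.

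**The case against.** The strongest reply is that no planned analysis is shown to be harmed. Section 6.3 gives t-tests for StimQ and regression models for BSID-III, and nothing for DialogPR-I. In section 6.2 the words tying endpoints to the randomised trial come before DialogPR-I, which sits next to the video themes. Section 9 foresees a paper validating parent report against video, for which a video-visit form is the natural one. The procedures in section 4.2 already collect what a fair comparison needs, so one descriptive sentence causes the trouble. This largely stands. It makes the harm conditional, but it does not say which schedule staff should follow or which record counts.

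Several stronger readings are tempting, and the documents do not support them:

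- **That the gap is 4 months.** Section 3.1.2 has families contacted, not filmed, on reaching 9-month eligibility. Four months is the top of the range for a second visit at 13 months.
- **That the place differs.** Sections 3.1.1 and 3.1.2 allow the same locations. Only the type of visit differs.
- **That filming or the interview changes the answers.** The plan does not say whether the form comes before or after them.
- **That the sub-study eligibility passages contradict each other.** Sections 3.4.2.1, 6.3 and 8.4.2 do not repeat the arm limit. That is silence, and sections 3.1.2 and 3.1.3.2 are explicit. If digital-arm families could in fact join, the imbalance would shrink.

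**Conclusion.** The point holds as a scheduling conflict with a conditional consequence. If section 5.1.7 governs, any between-arm comparison of DialogPR-I mixes book format with child age and visit type. The mean age difference is about 0.2–0.8 months with 10 filmed controls, 0.4–1.6 with 20 and 0.8–3.2 at the ceiling of 40. These figures assume 50 measured per arm, filming at 9 to 12 months, second visits at about 13 months in both arms, and video recruitment from the trial limited to the board-book arm.

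A reader might infer that the DialogPR-I result will be biased by a known amount, or that its false-positive rate is inflated. Neither follows. The documents do not say how scores change with age or visit type, so the effect on scores is unknown, and if section 4.2 governs the timing difference disappears. DialogPR-I is a pilot measure, and the primary endpoint, BSID-III, does not rest on it. The point still deserves correction before data collection, because second-visit forms not collected cannot be recovered.

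**What to change.** 1. In section 5.1.7, delete the clause that selects the earlier visit. Have all trial families complete DialogPR-I at the second visit, as the abstract and section 4.2 already provide. Externally recruited families, who have only the video visit, complete it there.
2. In section 6.2, state that the second-visit form is the trial endpoint.
3. Use video-visit forms only for the sub-study and for the validation work described in section 9.
4. Report a sensitivity analysis for prior exposure, or state it as a limitation. If families are to be left out, removing only filmed controls would set a selected control group against a complete digital arm. Sub-study agreement is given in the trial consent form (section 8.5) and assignment follows consent (section 3.1.3.1), so those who agreed can be removed from both arms.

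The cost is a few changes of wording and no added visit. Part of the problem remains. Filmed controls complete the form twice, and they alone reach the second visit having already seen it, read two e-book versions on film and been interviewed about reading. The change removes the difference in timing and visit type but not this difference in prior exposure, which is why step 4 is needed.

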#### **5.1.8 Demographic Questionnaire**

A brief set of questions used to collect demographic information about the participants.

#### **5.1.9 Standard Text Messages**

Standard text messages will be sent out to participants throughout the study. These text messages include an initial text message to welcome participants to the study, as well as text message reminders of upcoming well-child visits, to complete the emailed surveys, to download the e-book (digital arm participants only), and to schedule the final study visit. Additionally, text messages will be sent out to subjects who consented to participate in the videotape sub-study, reminding them of their study visit.

#### **5.1.10 Audio-recording and Videotaping of Interviews**

Parent-infant dyads recruited into the videotape sub-study will participate in a video recorded reading exercise and a brief, audio-recorded semi-structured interview. Parents will be videotaped while reading a print book and two versions (basic and enhanced) of an electronic book with their infant. As part of this exercise, parents will also be audio recorded while participating in a semi-structured one-on-one interview with a study team member. Videotaped book readings will be analyzed without transcription. Interview audio recordings will be transcribed by ADA Transcription (<http://www.adatranscription.com/>). Audio recordings will be de-identified and sent via their secure server, and subsequent transcripts will be saved on a secure server accessed only by members of the study team.

### **6 STATISTICAL CONSIDERATIONS**

#### **6.1 Primary Endpoint**

The primary endpoint for the randomized control trial will be the BSID-III scores at the second study visit when the child is between 12 and 18 months, 30 days of age.

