## **ABSTRACT**

### Context:

Reach Out and Read (ROR) has become a standard evidence-based primary care practice to support early literacy development of young at-risk children. It utilizes board books which are distributed at pediatric well visits along with literacy promotion and reading modeling by pediatricians. However, digital reading utilizing e-books and apps for reading on electronic devices has become popularized. We would like to address the important question of whether digital reading with e-books is as effective as reading with standard board books on early development. For this 18-month investigation, we propose to recruit 100 parent-infant dyads from 3 CHOP primary care pediatric practices (Indian Valley, Cobbs Creek and Roxborough). Healthy infants at least five months of age who are Medicaid eligible and whose parents have access to smart phones and other mobile digital devices at those practices would be recruited and randomized 1:1 to early literacy promotion using either 1) standard early reader board books or 2) digital electronic early reader books (e-books). Books would be distributed at 3 time points to coincide with well visits up to 13 months of age. Outcomes corresponding to reading behaviors (quantity and quality of joint reading) would be measured approximately 1 month after the 6, 9, and 12 month well visits. Child development would be measured when the child is between 12 and 18 months, 30 days of age. A subset of up to 40 parent infant dyads will be recruited to participate in a videotaped interaction while reading both an e-book and standard board book. Parent and child behaviors during the reading task will be coded and analyzed for differences across book type.

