### Objectives:

- 1) To test the effects of digital versus standard literacy promotion on early development using a randomized controlled trial design.
- 2) To explore the reading practices and reading activities among children and their parents when comparing the use of e-books to traditional board books.
- 3) To identify themes regarding dialogical reading behaviors among parents participating in the Video Sub-study.

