## **2 STUDY OBJECTIVES**

### **2.1 Primary Objective**

The primary objective of the study is to discover the effects of language development of young, at-risk children in digital versus standard literacy promotion using a randomized controlled trial design. In this instance we define standard as the use of age appropriate board books in literacy promotion initiatives and digital as the use of mobile app based e-book versions of the same board books in a literacy promotion intervention.

Specific Aim 1: To determine the comparative effectiveness of digital literacy promotion to standard literacy promotion on early development among young Medicaid eligible children in the Philadelphia metropolitan area.

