### 6.3 Statistical Methods

Summary statistics will be obtained, and differences between digital and standard arms will be assessed using intention-to-treat analysis. Cross-sectional differences in StimQ scores between digital and standard groups at the 6, 9 and 12 month well visits will be assessed using t-tests. To determine how the effects of digital versus standard literacy is associated with language development, we will develop regression models using longitudinal data methods that adjust for correlation in BSID-III scores over time and for potential confounding by demographic characteristics. To explore the impact of digital literacy on healthcare utilization, the EHR will be reviewed to identify a subjects' number of well visits and their vaccination history.

To determine whether parent adversity, health literacy, and/or parent mental health modify the effects of digital versus standard literacy on language development, we will develop similar regression models using longitudinal data methods, but we will also fit interaction terms between study group and ACE score ( $\geq 4$ ), SAHL (high or low) and EPDS score ( $> 10$ ). To determine if parent-child reading activity mediates the association of intervention group assignment and language development, we will use mediation analysis with separate models regressing group assignment on language development, parent-child reading activity on group assignment, and group assignment on language development adjusted for parent-child reading activity.

Assuming a mean cognitive subscale on the BSID-III of 96, a power of 0.70, an alpha of 0.05, and a clinically significant difference of 7.5 points on the BSID-III between groups, we estimate that we will need to recruit a total sample size of 100 eligible children (50 in each group) to participate in the main RCT study (Figure 1). To attain thematic saturation in the Video Sub-study, we will recruit up to 40 participants 9-12 months of age. These 40 participants may be recruited external to the main study if we are unable to recruit up to 40 from the 100 enrolled in the main study in a timely fashion. All analyses will be conducted using Stata Statistical Software, version 13 (College Station, TX).

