**Figure 1**

Power	n
0.60	80
0.65	90
0.70	100

Assuming a mean cognitive subscale of the BSID-III, an alpha of 0.05, and an SD of 15.

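### Section 6.1 does not say which BSID-III score is primary, and the Section 6.3 model for it assumes repeated BSID-III scores that the trial does not collect

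*Combined protocol and SAP*

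**What the plan says.** **Endpoint.** Section 6.1: "The primary endpoint for the randomized control trial will be the BSID-III scores at the second study visit". The word is plural, and neither a domain nor a score type is given. Section 5.1.6 describes an instrument with cognitive, language and motor parts. Section 6.2 lists no BSID-III score as secondary.

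**Objective.** Section 2.1: "The primary objective of the study is to discover the effects of language development of young, at-risk children". Specific Aim 1, in the same section, is broader: "To determine the comparative effectiveness of digital literacy promotion to standard literacy promotion on early development among young Medicaid eligible children". The abstract also speaks of early development.

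**Analysis.** Section 6.3, for language development: "we will develop regression models using longitudinal data methods that adjust for correlation in BSID-III scores over time". The effect-modification and mediation analyses in 6.3 also have language as the outcome. The t-tests in 6.3 are assigned to StimQ.

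**Sample size.** Section 6.3: "Assuming a mean cognitive subscale on the BSID-III of 96, a power of 0.70, an alpha of 0.05", with a difference of 7.5 points and 50 children per group. The note to Figure 1: "Assuming a mean cognitive subscale of the BSID-III, an alpha of 0.05, and an SD of 15".

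**Schedule.** The abstract (Study Interventions and Measures) and Sections 3.1.1, 4.2 and 6.1 place the BSID-III at the second study visit. The baseline lists in Sections 3.1.3.1 and 4.1 do not include it.

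**The concern.** A primary endpoint definition should settle, before any data are seen, which number decides the trial. Here a reader who follows the objective and the models would report language. The only places that name a particular BSID-III subscale name the cognitive one. If that choice is made after the scores are known, a nominal 0.05 does not cover it.

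The second gap is separate and would survive the first repair. The model class named for the BSID-III handles repeated scores within a child. With one score per child there is no correlation over time to model, so naming the score would still leave the primary comparison unspecified.

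**Working it through.** **1. What each place points to**

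| Place | Target |
|---|---|
| 6.1, endpoint | BSID-III scores, no domain |
| 2.1, objective | language |
| 6.3, main, effect-modification and mediation models | language |
| 3.1.3.1 and the 5.1.6 heading | BSID-III presented as the language measure |
| 3.1.4, intention-to-treat sentence | language |
| Aim 1, abstract, 3.1.1 intention-to-treat sentence | development in general |
| 6.3 sample size and Figure 1 note | cognitive |

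The weight of the text is on language. The definition in 6.1 does not say so.

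**2. Assessments per child.** One BSID-III at the second study visit and none at baseline, so 1 per child. The model in 6.3 needs at least 2.

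**3. The plan's own sample size.** Inputs: difference 7.5 (6.3), SD 15 (Figure 1 note), alpha 0.05 (both), 1:1 allocation. The sidedness is not stated. Two-sided is inferred because it reproduces Figure 1, whereas one-sided gives 76 in total for 0.70.

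Normal approximation: n per group = 2 × (15/7.5)² × (z for alpha + z for power)² = 8 × (z for alpha + z for power)².

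- Power 0.60: 8 × (1.960 + 0.253)² = 39.2, so 40 per group, 80 in total.
- Power 0.65: 8 × (1.960 + 0.385)² = 44.003 with unrounded quantiles, so 45 per group, 90 in total.
- Power 0.70: 8 × (1.960 + 0.524)² = 49.4, so 50 per group, 100 in total.

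All three rows of Figure 1 reproduce. The t-test (noncentral t) gives power 0.598, 0.650 and 0.697 at totals of 80, 90 and 100. The mean of 96 does not appear in the formula.

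**4. Illustration: two scores, each tested at two-sided 0.05.** The plan does not say this will happen, and the correlations are assumed. Chance of at least one false positive = 1 − P(|Z1| ≤ 1.96 and |Z2| ≤ 1.96).

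- Correlation 0: 1 − 0.95² = 0.0975, or 9.8%.
- Correlation 0.5: 0.0907, or 9.1%.
- Correlation 0.7: 0.0835, or 8.3% (0.08345 before rounding).

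**5. Illustration: keeping two primary scores at 0.025 each (Bonferroni, assumed).** Power per score at 50 per group falls from 0.697 to 0.590 (t-test). For power 0.70 the normal approximation gives 8 × (2.241 + 0.524)² = 61.2, so 62 per group. Totals compared under one rule at a time:

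| Method | One score at 0.05 | Two scores at 0.025 |
|---|---|---|
| Normal approximation | 100 | 124 |
| t-test, rounded up to reach 0.70 | 102 | 126 |

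**The case against.** The best reply is that language is plainly meant. It is the outcome in 2.1, in every 6.3 model of child development, in the 3.1.4 analysis sentence and in the heading of 5.1.6. No model has a cognitive outcome, so reporting cognitive as primary would depart from both 2.1 and 6.3. This stands in part: the two scores are not equally open, and a reader who infers a free choice between them goes beyond the text. But a lean is not a designation. Section 6.1 is the controlling text and names no score.

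The cognitive label is also thin. In 6.3 it attaches to the mean, which does not affect the sample size, and the 7.5-point difference is given for the BSID-III without a subscale. A reader might infer that the trial is underpowered for language. The documents do not support that: they give no separate SD or difference for language, and the calculation is correct for its inputs.

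A reader might also treat the early-development wording as a contradiction (the abstract's question is "whether digital reading with e-books is as effective as reading with standard board books on early development" and its first objective "To test the effects of digital versus standard literacy promotion on early development using a randomized controlled trial design"). It is an umbrella term that includes language, and an aim may be broader than its endpoint.

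On the model, some longitudinal methods reduce to ordinary regression when each child has one record, so the analysis could be rescued in practice. The plan does not say this, and its stated reason for the method, correlation over time, does not exist for this outcome.

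Finally, Appendix 7 is not shown. The finding that no score is designated covers the visible text only.

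**Conclusion.** The point holds as a defect of specification that must be fixed. The primary BSID-III score is not designated, the sample-size label disagrees with the objective and models, and the stated BSID-III analysis assumes repeated scores where one per child is scheduled.

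Its size cannot be given as a realised error rate. The 8.3% to 9.8% figure applies only if language and cognitive were both tested at an unadjusted 0.05, and it rests on assumed correlations. A reader might infer that the plan intends such testing, but nothing in it says so. The sample size is not in error. With a single designated score, 100 children give the stated power of about 0.70, provided SD 15 and 7.5 points apply to that score.

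**What to change.** 1. **Sections 6.1 and 6.2.** Designate one BSID-III score, with its score type, at the second study visit as the single primary endpoint, tested at two-sided 0.05. Language fits 2.1 and 6.3; the sponsor should confirm. List the other domain scores as secondary in 6.2.
2. **Section 6.3, analysis.** Replace the longitudinal model with a between-arm comparison of that score at the single time point, for example a linear model adjusted for clinic site (the stratification factor in 3.2), with any demographic covariates listed in advance. Make the same change in the effect-modification models, which 6.3 builds in the same way.
3. **Section 6.3, sample size, and the Figure 1 note.** Relabel for the designated score, and state SD 15 and 7.5 points as assumptions for it.

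Rewording the broader terms in the abstract, Specific Aim 1 and 3.1.1 is optional.

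**Cost.** Text changes only, with no added visit or assessment, and the sample size stays at 100. The trade-off is that an effect confined to a non-designated domain could not be called the primary result.
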